9.3. Pharmacokinetic Analyses

9.3.1. Overview of Planned Pharmacokinetic Analyses

The pharmacokinetic (PK) analyses will be based on the “Pharmacokinetic Parameter” population, unless otherwise specified.

Table 6 provides an overview of the planned analyses with full details being presented in [Appendix 11: List of Data Displays](#).

Table 6 Overview of Planned Pharmacokinetic Analyses

Endpoints	Untransformed				Log-Transformed			
	Summary		Individual		Summary		Individual	
	F	T	F	L	F	T	F	L
Plasma Drug Concentrations	Y ^{[2][3]}	Y ^[3]	Y ^[1]	Y	Y ^{[2][3]}			
Derived PK Parameters		Y ^[3]		Y		Y ^[3]		

NOTES :

- T = Table, F = Figures, L = Listings, Y = Yes display generated.
- Stats Analysis = Represents TFL related to any formal statistical analyses (i.e. modelling) conducted.
- Summary = Represents TFL related to any summaries (descriptive statistics) of the observed raw data.
- Individual = Represents FL related to any displays of individual subject observed raw data.
- 1. Linear and Semi-Log plots will be created on the same display.
- 2. Mean (Linear and Semi-Log on same display) and Median (Linear and Semi-Log on same display) plots will be created.
- 3. Displays generated using the 'PK parameter populations.

9.3.2. Drug Concentration Measures

Refer to [Appendix 4: Data Display Standards & Handling Conventions \(Section 11.4.3 Reporting Process & Standards\)](#).

9.3.3. Pharmacokinetic Parameters

9.3.3.1. Deriving Pharmacokinetic Parameters

- Refer to [Appendix 4](#): Data Display Standards & Handling Conventions (Section [11.4.3](#) Reporting Process & Standards).
- The pharmacokinetic parameters will be calculated by standard non-compartmental analysis according to current working practices and using Win Nonlin.
- All calculations of non-compartmental parameters will be based on actual sampling times.

Table 7 Derived Pharmacokinetic Parameters

Parameter	Parameter Description
First and Second last Dose in each treatment period as data permit	
AUC(0-tau)	Area under the concentration-time curve over the dosing interval after first and last dose
Cmax	Maximum observed concentration, determined directly from the concentration-time data on Day 1 and Day 7.
tmax	Time to reach Cmax, determined directly from the concentration-time data.
If Assessable	
Lamda_z	Terminal phase rate constant
t½	Apparent terminal half-life will be calculated as: $t\frac{1}{2} = \ln 2 / \text{Lambda}_z$

NOTES:

- Additional parameters may be included as required.

11. APPENDICES

Section	Appendix
RAP Section 5 : Analysis Populations	
Section 11.1	Appendix 1 : Protocol Deviation Management and Definitions for Per Protocol Population
RAP Section 6 : General Considerations for Data Analyses & Data Handling Conventions	
Section 11.2	Appendix 2 : Time and Events
Section 11.3	Appendix 3 : Treatment States & Phases
Section 11.4	Appendix 4 : Data Display Standards & Handling Conventions 
 • Study Treatment & Sub-group Display Descriptors • Baseline Definitions & Derivations • Reporting Process & Standards
Section 11.5	Appendix 5 : Derived and Transformed Data 
 • General, Study Population & Safety • Efficacy • Pharmacokinetic • Pharmacodynamic / Biomarkers
Section 11.6	Appendix 6 : Premature Withdrawals & Handling of Missing Data 
 • Handling of Missing Dates • Handling of Partial Dates
Section 11.7	Appendix 7 : Values of Potential Clinical Importance 
 • Laboratory Values • ECG's • Vital Signs
Section 11.8	Appendix 8 : Laboratory A&R Datasets
Section 11.9	Appendix 9 : Biomarker A&R Datasets
Other RAP Appendices	
Section 11.10	Appendix 10 : Abbreviations & Trade Marks
Section 11.13	Appendix 11 : List of Data Displays
Section 0	Appendix 12 : Example Mock Shells for Data Displays

11.1. Appendix 1: Protocol Deviation Definitions for Per Protocol Population**11.1.1. Exclusions from Per Protocol Population**

A subject meeting any of the following criteria will be excluded from the Per Protocol population:

Number	Exclusion Description
01	Subject takes prohibited Concomitant Medications
02	Others as defined in the PDMP

11.2. Appendix 2: Time and Events

Appendix 2: Time and Events

Procedure	Screening Period	Treatment Periods I and II (Day)										Follow-up
	Day -25 to Day -1 prior to Period I	-1	1	2	3	4	5	6	7	8	9	
Informed consent	X											
Inclusion and exclusion criteria	X											
Demography	X											
Full physical examination including height & weight	X											
Brief physical exam including weight		X				X			X			X
Medical history/Medication history	X											
Hepatitis B & C screen	X											
Echocardiogram	X											
Urine drug and alcohol breath test	X	X										
Clinical lab assessments ¹⁴	X	X				X			X			X
NT-proBNP	X	X							X			
Serum CTX ¹¹		X							X			
Fecal Occult Blood Test ¹²	X								X			
Pharmacokinetic sample ¹		X	X	X	X	X	X	X	X	X	X	
Digoxin sample ²		X	X	X	X	X	X	X	X			X
Troponin	X	X		X		X			X			X
DLco/DLno ¹⁰	X	X				X	X	X	X			X
12-lead ECG/time & frequency domains ³	X ⁹	X ⁹				X			X			X

CONFIDENTIAL

201881

Procedure	Screening Period	Treatment Periods I and II (Day)										Follow-up
		Day -25 to Day -1 prior to Period I	-1	1	2	3	4	5	6	7	8	
Vital signs	X	X	X	X	X	X	X	X	X			X
Weight			X	X	X		X	X				
Genetic sample		For subjects who provide consent, sample collected after start of treatment										
Study treatment ⁴			X	X	X	X	X	X	X			
AE/SAE review	X		←=====→									X
Concomitant med review	X		←=====→									X
Pulmonary function tests	X					X				X		X
Step exercise test/breath-by-breath gas exchange	X									X		X
Dyspnea assessment	X						X			X		X
Orthopnea							X					
SF-36 Acute	X								X			X
Polysomnography including oximetry (Sleep Apnea Clinic) ^{5,13}		←=====→								←=====→		
Plasma and 8-hour urine catecholamines ⁶	X								X			
Saline infusion							X	X				
Admission to CRU ⁷		X										
Discharge from CRU ⁷				X								
Meals ⁸	X	X	X	X	X	X	X	X				
Appetite Assessment (SNAQ)	X					X				X		X
CSSRS (Suicidality)	X									X		X
Audiometry	X ¹³									X		X
BodyGuardian Monitor (Preventice)		←=====Continuous=====→										

1. Pharmacokinetic samples to determine GSK2798745 and any metabolite(s) concentrations will be obtained at the following times on Day 1 of each treatment period: Predose, 0.5, 1, 1.5, 2, 3, 5, 8 and 12 hours and at the following times on Day 7 of each treatment period: Predose, 0.5, 1, 1.5, 2, 3, **and 5 and 10** hours. On Day 2 of each treatment period, samples will be collected predose and at 12 hours post dose. On Days 3 through 6, PK samples will be collected predose. **On Days 8 and 9, samples will be collected at 24 and 48 hours, respectively, after the last dose of study medication administered on Day 7.** The time points may be modified based on emerging data. Some of these timepoints may also be utilized to collect samples to determine concentrations of other medications (e.g., atorvastatin and/or simvastatin). See the SRM for detailed information.
2. Digoxin concentrations will be monitored only in those subjects who are taking digoxin
3. Time and frequency domains assessed by ECG obtained on Day -1 and Day 7
4. Subjects will remain in the CRU for a minimum of 4 hours after each administration of study medication. [Note: The first 6 subjects enrolled will remain in the CRU for 52 hours after the first dose of study medication in each period]
5. Only for subjects participating in the sub-study: At Day -1 of the first study period only, subjects will undergo an overnight sleep study. Only those subjects who are participating in the sub-study with sleep disordered breathing will undergo additional sleep studies on Day 6 of both study Periods I and II.
6. Only for subjects participating in the sub-study: Urinary norepinephrine (NE) and epinephrine (E) concentrations will be determined from 8-hour collections obtained during the overnight sleep study; urinary creatinine will also be measured to normalize the NE and E concentrations. A blood sample to determine plasma concentrations of NE and E will be obtained the morning after the sleep study between the hours of 9:00 am and 10:00 am after the subject has been supine for 20 minutes in a quiet room.
7. The first 6 subjects enrolled will remain in the CRU for two days (Day 1 and Day 2) after the first dose of study medication in each period.
8. Three meals per day will be provided by the dietary department either in the CRU or as a boxed meal(s) to take home.
9. ECGs to be performed in triplicate
10. On the days where exercise or the saline infusion is performed, DLco/DLno will be completed just prior to and after both exercise and the saline infusion.
11. **Blood sample for analysis of Serum CTX must be collected when the subject is fasting.**
12. **Fecal Occult Blood Test (FOBT) cards will be provided to subjects at the end of the screening visit and must be completed and sent back to the laboratory prior to the baseline visit according to the laboratory's standard collection procedures. Similarly, subjects will be given FOBT cards at the end of the Day 7 visit of each study period with completion instructions.**
13. **Day -1 audiology and sleep study assessments may be completed 7 days prior to Day -1.**
14. **Clinical laboratory assessments will be collected as a fasting sample.**

11.3. Appendix 3: Treatment States and Phases

11.3.1. Treatment Phases

Assessments and events will be classified according to the time of occurrence relative to study treatment, unless otherwise specified.

Treatment Phase	Definition
Pre-Treatment 1	Date < Study Treatment Start Date for Period 1
On-Treatment 1	Study Treatment Start Date for Period 1 ≤ Date ≤ Study Treatment Stop Date for Period 1
Post-Treatment 1	Date > Study Treatment Stop Date for Period 1
Pre-Treatment 2	Date < Study Treatment Start Date for Period 2
On-Treatment 2	Study Treatment Start Date for Period 2 ≤ Date ≤ Study Treatment Stop Date for Period 2
Post-Treatment 2	Date > Study Treatment Stop Date for Period 2

11.3.2. Treatment States

Assessments and events will be classified according to time of occurrence relative to the start and/or stop date of the study treatment.

11.3.3. Treatment States for AE Data

Treatment State	Definition
AE = Pre-Treatment	AE Start Date < Study Treatment Start Date
AE = On-Treatment	If AE onset date is on or after the treatment start date and on or before the treatment stop date. Study Treatment Start Date ≤ AE Start Date ≤ Study Treatment Stop Date [+ 1]
AE = Post-Treatment	If AE onset date is after the treatment stop date. AE Start Date > Study Treatment Stop Date + 1
AE Onset Time Since 1 st Dose (Days)	If Treatment Start Date > AE Onset Date : = AE Onset Date - Treatment Start Date If Treatment Start Date ≤ AE Onset Date : = AE Onset Date – Treatment Start Date + 1 Missing otherwise
AE Duration (Days)	AE Resolution Date – AE Onset Date + 1
AE = Drug-related	If relationship is marked 'YES' on [Inform/CRF OR value is missing.

NOTES:

- If the study treatment stop date is missing then the AE will be considered to be On-Treatment

11.4. Appendix 4: Data Display Standards & Handling Conventions

11.4.1. Study Treatment & Sub-group Display Descriptors

Study Treatment Descriptions			
RandAll NG		Data Displays for Reporting	
Code	Description	Description	Order
A	GSK2798745 2.4 mg	GSK 2.4 mg	2
P	Placebo	Placebo	1

11.4.2. Baseline Definition & Derivations

11.4.2.1. Baseline Definitions

For all endpoints baseline value will be taken on Day -1 for each treatment period, unless otherwise specified.

11.4.2.2. Derivations and Handling of Missing Baseline Data

Definition	Reporting Details
Change from Baseline	= Post-Dose Visit Value – The corresponding Baseline
[% Change from Baseline]	= [(Post-Dose Visit Value – Baseline) / Baseline] x 100]

NOTE :

- Unless otherwise specified, the baseline definitions specified in [11.4.2.1Baseline Definitions](#) will be used for derivations for endpoints / parameters and indicated on summaries and listings.
- Unless otherwise stated, if baseline data is missing no derivation will be performed and will be set to missing.
- The baseline definition will be footnoted on all change from baseline displays.

11.4.3. Reporting Process & Standards

Reporting Process	
Software	

 The currently supported versions of Spotfire, SAS and R software will be used to perform all data analyses, generate tables, figures, and listings. 	
Reporting Area	
HARP Server	: US1SALX00259
HARP Area	: \arprod\gsk2798745\mid201881\final_01
QC Spreadsheet	: \arprod\gsk2798745\mid201881\final_01\documents
Analysis Datasets	

 Analysis datasets will be created according to Integrated Data Standards Library standards. 	

Reporting Standards	
General	

 • The current GSK Integrated Data Standards Library (IDSL) will be applied for reporting, unless otherwise stated: 
 • 4.03 to 4.23: General Principles • 5.01 to 5.08: Principles Related to Data Listings • 6.01 to 6.11: Principles Related to Summary Tables • 7.01 to 7.13: Principles Related to Graphics 	
Formats	

 • All data will be reported according to the actual treatment the subject received unless otherwise stated. • GSK IDSL Statistical Principles (5.03 & 6.06.3) for decimal places (DP's) will be adopted for reporting of data based on the raw data collected. • Numeric data will be reported at the precision collected on the eCRF. • The reported precision from non eCRF sources will follow the IDSL statistical principles but may be adjusted to a clinically interpretable number of DP's. 	
Planned and Actual Time	

 • Reporting for tables, figures and formal statistical analyses : 
 • Planned time relative to dosing will be used in figures, summaries, statistical analyses and calculation of any derived parameters, unless otherwise stated. • The impact of any major deviation from the planned assessment times and/or scheduled visit days on the analyses and interpretation of the results will be assessed as appropriate. • Reporting for Data Listings: 
 • Planned and actual time relative to study drug dosing will be shown in listings (Refer to IDSL Statistical Principle 5.05.1). • Unscheduled or unplanned readings will be presented within the subject's listings. • Visits outside the protocol defined time-windows (i.e. recorded as protocol deviations) will be included in listings but omitted from figures, summaries and statistical analyses. 	
Unscheduled Visits	

 • Unscheduled visits will not be included in summary tables or figures, unless otherwise stated. • All unscheduled visits will be listed. 	
Descriptive Summary Statistics	
Continuous Data	Refer to IDSL Statistical Principle 6.06.1
Categorical Data	N, n, frequency, %

Reporting of Pharmacokinetic Concentration	
Descriptive Summary Statistics	Refer to IDSL Statistical Principle 6.06.1 Assign zero NQ values (Refer to GUI_51487 for further details)
Reporting of Pharmacokinetic Parameters	
Descriptive Summary Statistics (Log Transformed Data)	N, n, geometric mean, 95% CI of geometric mean, standard deviation (SD) of logged data and between geometric coefficient of variation (CV _{b/w} (%)): $CV_b (\%) = \sqrt{(\exp(SD^2) - 1)} * 100$ (NOTE: SD is the SD of log transformed data)
Parameters Not Being Log Transformed	tmax, first point, last point and number of points used in the determination of Lambda_λz.
Parameters Not Being Summarised	tmax, first point, last point and number of points used in the determination of Lambda_λz.
Listings	Include the first point, last point and number of points used in the determination of Lambda_λz.
Graphical Displays	

 Refer to IDSL Statistical Principles 7.01 to 7.13. 	

11.5. Appendix 5: Derived and Transformed Data

11.5.1. General

Multiple Measurements at One Time Point

- Mean of the measurements will be calculated and used in any derivation of summary statistics but if listed, all data will be presented.
- For DLco standard practice is to attempt three measures. A pulmonologist will indicate which of the three measures are valid, and then a mean will be taken of all valid measures to be used as the measurement for that time point. If there is only one valid measure, that measure will be used.

Study Day

- Calculated as the number of days from randomisation date:
 - [1] Ref Date = Missing → Study Day = Missing
 - [2] Ref Date < Randomisation Date → Study Day = Ref Date – Randomisation Date
 - [3] Ref Date ≥ Randomisation Date → Study Day = Ref Date – (Randomisation Date) + 1

11.5.2. Study Population

Demographics

Age

- GSK standard IDSL algorithms will be used for calculating age where birth date will be imputed as follows:
 - [1] Any subject with a missing day will have this imputed as day '15'.
 - [2] Any subject with a missing date and month will have this imputed as '30th June'.
- Birth date will be presented in listings as 'YYYY'.

Body Mass Index (BMI)

- Calculated as **Weight (kg) / [Height (m)]²**

Extent of Exposure

- Number of days of exposure to study drug will be calculated using dates from the trial medication form. The duration of exposure in days will be based on the formula:
Duration of Exposure in Days = Treatment Stop Date – (Start Date + 1)
- Subjects who were randomized but did not report a treatment start date will be categorized as having zero days of exposure. The cumulative dose will be based on the formula:
Cumulative Dose = Sum of (Number of Days x Total Daily Dose)
- If there are any treatment breaks during the study, then the exposure data will be adjusted accordingly.

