4.2. Treatment Arms, Duration and Assessments

Approximately 14 days (up to 25 days) before the start of Period I, subjects will begin a screening evaluation to determine eligibility for entry into the study. Eligible subjects will be randomized to one of two treatment sequences. Subjects will receive either GSK2798745 2.4 mg or placebo once daily for a period of 7 days. After at least a 14-day

washout period (preferably not greater than 30 days from last dose in Period I), subjects will participate in a second, identical 7-day treatment period and receive the alternate study medication.

During both study periods, the first 6 subjects will remain in the unit (i.e. clinical research unit, CRU) overnight for the first 2 days (Days 1 and 2) to allow for continuous safety monitoring. Subsequently, these initial subjects will remain in the unit for a minimum of 4 hours after the administration of study medication (Days 3 through 7). All subjects will be equipped with the Preventice BodyGuardian for continuous remote monitoring of ECG, heart rate, and respiration rate (Day -1 to Day 7). Subjects may remain in the unit for the duration of each of the 7 day treatment periods for convenience.

After the first 6 randomized subjects have completed the two-day, in-house safety monitoring during Periods I and II, subsequent subjects enrolled into the study will remain in the unit for a minimum of 4 hours after the administration of study medication on all study days (Days 1 through 7). However, subjects may remain in the unit for the duration of each of the 7 day treatment periods as determined on a case by case basis with the Investigator(s). This is not a requirement for successful completion of the study, but is mainly for purposes of subject convenience only.

Prior to the start of each study period, all subjects will undergo an assessment of pulmonary function testing (PFTs), gas transfer measurements including DLco, DLno and Vc, breath-by-breath measurements of minute ventilation, O₂ consumption and VCO₂ production during a metered 3-minute step exercise to establish ventilatory efficiency (V_E/VCO₂), and a dyspnea assessment. Additionally, a measurement of N-terminal pro-B-type Natriuretic Peptide (NT-proBNP) concentration, clinical laboratory tests, patient-reported health status (SF-36 Acute), and general safety assessments will be obtained.

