3.3. Study Design

Overview of Study Design and Key Features	

Period I
 
Period II
 
Screening → GSK2798745 7 days or Placebo 7 days → 14-day Washout → GSK2798745 7 days or Placebo 7 days → Follow-up
 
Legend:
 
 Sleep Study (Optional) DLco (PFTs) Exercise DLco* Saliva Infusion* 
*Eligible Subjects Only
	
Design Features	
 This is a randomized, double-blind, sponsor-unblinded, placebo-controlled, 2 X 2 crossover study in adults with heart failure. The

Overview of Study Design and Key Features	
	
study will be conducted at multiple centers.
 
 Subjects have an at least 3 month history of HF, be a NYHA Class II-IV, a NT-proBNP of greater than 400 pg/ml within the last 6 months and a % predicted DLco of < 80% at screening.
Dosing	
 Subjects are dosed once daily for 7 days. Then there is a wash out period of at least 14 days, followed by another 7 days of once daily dosing.
Treatment Assignment	
 Eligible subjects will be randomized to one of two treatment sequences. A sufficient number of subjects with heart failure will be enrolled so that 12 subjects complete the two study periods and critical assessments. Subjects will receive either GSK2798745 or placebo once daily for a period of 7 days. After at least a 14-day washout period (preferably not greater than 30 days from last dose in Period I), subjects will participate in a second, identical 7-day study period and receive the alternate study medication.
Interim Analysis	
 After approximately 5-6 subjects complete both study periods, a sponsor unblinded interim analysis will be performed. After approximately 9 subjects complete both study periods, a sponsor unblinded interim analysis will be performed. After 12 subjects complete both study periods, prior to SAC, an interim analysis will be performed to determine if additional subjects will be enrolled in the study (up to 24 subjects). Full details are in Section 3.1

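### A misplaced bracket in the SAP exposure formula makes a full 7-day course count as 5 days and a single dosing day as -1

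*SAP*

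**What the plan says.** Under Extent of Exposure, SAP section 11.5.2 takes dates from the trial medication form and applies "Duration of Exposure in Days = Treatment Stop Date – (Start Date + 1", where the bracket closes after the 1. The same section then states: "Subjects who were randomized but did not report a treatment start date will be categorized as having zero days of exposure". It defines cumulative dose as a sum of number of days times total daily dose, and says exposure will be adjusted for treatment breaks.

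Two other derivations in the SAP count days inclusively. Adverse event duration (section 11.3.3) is "AE Resolution Date – AE Onset Date + 1". Study Day on or after randomisation (section 11.5.1) is "Ref Date – (Randomisation Date) + 1", where the bracket closes before the + 1.

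The planned course is 7 daily doses per period. SAP section 3.3 says "Subjects are dosed once daily for 7 days", and Protocol section 4.2 says "Subjects will receive either GSK2798745 2.4 mg or placebo once daily for a period of 7 days", with dosing on Days 1 through 7. Treatment dates are defined by period in SAP section 11.3.1, for example "Study Treatment Start Date for Period 1 ≤ Date ≤ Study Treatment Stop Date for Period 1". Section 11.4.3 adds: "All data will be reported according to the actual treatment the subject received unless otherwise stated".

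**The concern.** The bracket puts the + 1 on the start date, so 1 is subtracted where it should be added. The formula therefore cannot return the 7 days that the design prescribes, and for very short courses it returns values that make no sense.

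Table 3.01 and Listing 11 both use the All Subjects population, whose members have all taken at least one dose (SAP section 5). For a period in which dosing took place, 0 or -1 days cannot be right. Zero is also the value the SAP gives when no treatment start date is reported. A dosed subject with no Period II start date would plausibly be set to zero for that period, and would then look the same as someone who took two doses in it.

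What is at stake is the accuracy of a descriptive safety display, not an efficacy conclusion.

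**Working it through.** **Inputs**
- Formula as written: stop − (start + 1), SAP section 11.5.2.
- Inclusive form: stop − start + 1, as in SAP sections 11.3.3 and 11.5.1.
- Planned course: Days 1 to 7 in each period, Protocol section 4.2 and SAP section 3.3.
- Planned active dose: 2.4 mg per day, Protocol section 4.2.

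**General result**

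As written minus inclusive = (stop − start − 1) − (stop − start + 1) = −2, whatever the dates.

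**Applied within one period, starting on Day 1**

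| Last dosing day | As written | Inclusive |
|---|---|---|
| 7 | 7 − (1 + 1) = 5 | 7 − 1 + 1 = 7 |
| 4 | 4 − (1 + 1) = 2 | 4 − 1 + 1 = 4 |
| 2 | 2 − (1 + 1) = 0 | 2 − 1 + 1 = 2 |
| 1 | 1 − (1 + 1) = −1 | 1 − 1 + 1 = 1 |

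The planned figure of 7 days is not reproduced by the formula as written. It is reproduced by the inclusive form. The relative error for a full course is −2/7 = −29%.

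**Could the stop date explain it?** If the stop date were recorded as the day after the last dose, a full course would give 8 − (1 + 1) = 6, which is still not 7.

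**Applied to one span over both periods.** Assume a 14-day washout, the planned minimum. Dosing then runs from Day 1 to Day 7 + 14 + 7 = 28. As written this gives 28 − 2 = 26 days, against 28 inclusively. After removing the 14 washout days it gives 12 against 14, an error of −2/14 = −14%. The shortfall is again 2 days, now once per subject instead of once per period.

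**Cumulative dose, only if this duration supplies the number of days.** The SAP does not say that it does. If it does, a full active period gives 5 × 2.4 = 12.0 mg instead of 7 × 2.4 = 16.8 mg, and a single active dose gives −1 × 2.4 = −2.4 mg instead of 2.4 mg.

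**The case against.** The strongest objection is that the figures of 5 and −1 rest on an inference. Section 11.5.2 puts no period label on the start and stop dates. Section 11.3.1 classifies assessments and events by phase and does not define exposure. The treatment-break sentence could be how the washout is meant to be removed from a single span. All of this is fair, and the SAP should state which reading applies. But reporting by treatment received in a crossover needs a count for each period, and the single-span reading is also 2 days short. The break sentence does not move the bracket.

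A second objection concerns the overlap at zero. A randomized subject who was never dosed is outside the All Subjects population and so appears in neither display. That is correct, and it narrows the problem. The overlap arises only if a dosed subject has no start date for a period and the zero rule is applied to that period, which is plausible but not stated.

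Third, the practical effect is small. On the per-period reading the shift is the same for active and placebo, so the comparison between them is not biased. Short courses require early withdrawal. A negative duration would probably be noticed in quality control, and the inclusive formulas elsewhere make the intent clear. This limits the weight of the point. It does not make the formula right: code that follows the SAP gives wrong numbers, and code that gives right numbers departs from the SAP.

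**Conclusion.** The formula is wrong as written, and nothing else in either document corrects it. The shortfall is exactly 2 days for any pair of dates. Applied per period, a full course shows 5 days instead of 7, two dosing days show 0 and one shows −1.

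The 2-day shortfall rests on no assumption. Its appearance in every treated period rests on the per-period reading, which the SAP supports without stating. The cumulative-dose figures depend on a link that the SAP does not make explicit.

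Severity is minor. The effect is confined to Table 3.01, Listing 11 and possibly cumulative dose. Adverse event classification has its own date rules, and the DLco analysis does not use exposure duration.

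**What to change.** In SAP section 11.5.2, replace the formula with: Duration of Exposure in Days = Treatment Stop Date − Treatment Start Date + 1. State that it is computed within each treatment period. If this duration is the number of days in the cumulative dose formula, say so and use the corrected count there.

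The cost is a one-line correction and a check of the code behind Table 3.01 and Listing 11. No new data are needed: the derivation already draws on the trial medication form, and Protocol section 6.6 requires the date and time of every clinic dose to be recorded.
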